6.3. Treatment Discontinuation and Withdrawal from the Trial

Given this rare patient population, every effort should be made to encourage and keep patients enrolled in the trial until completion, unless there are any safety concerns necessitating withdrawal of the patient. The Sponsor will provide assistance for patient and caregiver travel and will provide other necessary logistical support to ease the burden on the patient in order to facilitate compliance and completion of trial participation.

Discontinuation of trial treatment or skipped visits/injections may be allowed without withdrawal from the trial.

Some patients' reason for discontinuation may be related to injection site reactions and burdensome laboratory/visits. Patients can be offered the option to discontinue trial medication but remain in the trial. These patients who stop therapy will be counted as a non-responder, irrespective of treatment assignment. However, they will be followed and have weight assessments at each visit, particularly at the final visit to determine weight trajectory for all patients. Patients who withdraw before completing Visit 14 are to attend an Early Termination visit within 14 days (± 7 days) after the last dose of trial medication for final trial assessments. If possible, patients will be asked to determine weight assessment at the expected time of their EOT visit.

If the patient withdraws consent for disclosure of future information, the Sponsor may retain and continue to use any data collected before such a withdrawal of consent.

If a patient withdraws from the trial, he/she may request destruction of any samples taken and not tested, and the Investigator must document this in the site trial records.

Patients will be informed that they have the right to withdraw from the trial at any time for any reason, without prejudice to their medical care. The Investigator also has the right to withdraw patients from the trial for reasons such as:

- AEs, which in opinion of Investigator justifies treatment or trial withdrawal. For specific predefined events, additional monitoring and guidance for the Investigator is provided in [Appendix 5](#).
- Non-adherence to trial medication regimen or protocol requirements.
- Non-compliance with instructions or failure to return for follow-up.
- Note: The Sponsor may choose to discontinue investigation of a particular genetic cohort/variant at any time; therefore, continued participation of patients for that genetic cohort/variant will be addressed at that time

All patients withdrawn prior to completing the treatment period should be strongly encouraged to complete the Early Termination visit as outlined in the SoA ([Table 1](#) and [Table 2](#)), even if they are no longer receiving trial medication.

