5.1.3.1. End of Treatment and End of Study

The End of Treatment Visit will occur as an in-person clinic visit on Study Day 112 for patients who complete only Stage 1 or on Study Day 280, which is the final day of treatment with setmelanotide or placebo for patients who complete Stage 2. A final End of Study (EOS) Visit will occur 4 weeks after the EOT visit. The EOS Visit will be conducted via telephone. At the end of Stage 2, patients may be offered the option of enrolling into a long-term extension (LTE) trial. If required by local regulation or if deemed necessary to assess patient safety by physical examination or after a longer follow-up period, the EOS Visit may be converted to an in-person visit, and/or can occur up to Week 48.

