6.4. Lost to Follow-up

Patients are considered as being lost to follow-up if they fail to return for scheduled evaluations and cannot be contacted by the site. The following actions must be taken if the patient fails to return to the clinic for a required trial evaluation:

- The trial site must attempt to contact the patient and reschedule the missed evaluation as soon as possible and counsel the patient on the importance of maintaining the assigned evaluation schedule.
- Before a patient is deemed lost to follow-up, the Investigator or designee must make every effort to regain contact with them or next of kin by, for example, repeat telephone calls, certified letter to the patient's last known mailing address, or local equivalent methods. At least 3 unique documented contact attempts to follow-up over a period of weeks to months should be made, including at least 1 in relation to the final visit on Day 308. The patient should only be permanently recorded as lost to follow-up if they did not respond to any contact attempts by Day 308. These contact attempts should be documented in the patient's medical records.

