	
[REDACTED]
 
[REDACTED]
	
[REDACTED]
 
[REDACTED]
 
[REDACTED]
 
[REDACTED]
 
[REDACTED]
 
[REDACTED]
 
[REDACTED]
 
[REDACTED]

	
[REDACTED]
 
[REDACTED]
 
[REDACTED]
 
[REDACTED]
 
[REDACTED]
	
[REDACTED]
 
[REDACTED]
 
[REDACTED]
 
[REDACTED]
 
[REDACTED]
 
[REDACTED]
 
[REDACTED]
 
[REDACTED]
 
[REDACTED]
 
[REDACTED]
 
[REDACTED]

	
[REDACTED]
 
[REDACTED]
 
[REDACTED]
 
[REDACTED]
 
[REDACTED]
 
[REDACTED]
 
[REDACTED]
 
[REDACTED]
	
[REDACTED]
 
[REDACTED]
 
[REDACTED]
 
[REDACTED]

	
[REDACTED]
 
[REDACTED]
 
[REDACTED]
 
[REDACTED]
 
[REDACTED]
 
[REDACTED]
	
[REDACTED]
 
[REDACTED]
 
[REDACTED]
 
[REDACTED]
 
[REDACTED]
 
[REDACTED]
 
[REDACTED]
 
[REDACTED]
 
[REDACTED]

	Objectives	Endpoints
Safety	To evaluate the safety and tolerability of setmelanotide in patients with genetic variants in the MC4R pathway	Safety and tolerability assessed by the frequency and severity of AEs, changes in vital signs, and changes in laboratory evaluations at the end of Stage 1 and Stage 2

A. Estimand

Attribute	Description
Treatment	Setmelanotide
Population	Patients between ages of 6 and 65 with Specific Gene Variants in the Melanocortin-4 Receptor Pathway
Endpoint	Achieving a $\geq 5\%$ reduction in BMI from Baseline at the end of Stage 1
Intercurrent Events	For Discontinuation of randomized treatment or use of a rescue medication if any, Treatment policy strategy will be implemented.
Population-level Summary	Proportion of patients achieving a $\geq 5\%$ reduction in BMI from Baseline at the end of Stage 1

III. Study Design

A. Design Overview

This is a 2-stage (open-label stage followed by a randomized double-blind, placebo-controlled stage) Phase 2 trial of setmelanotide in patients with obesity with specific gene variants in the MC4R pathway. Approximately 100 patients between the ages of 6 and 65 years, inclusive, are planned to be enrolled in Stage 2 of the trial with up to 200 patients enrolled in Stage 1 (open-label).

Stage 1 (Open Label)

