1	Virtual Visit 6	12	84	71 - 98
1/2	In-Person Clinic Visit 7	16/End of Stage 1	112	Patients enrolling in Stage 2: 99 to first dose of Stage 2 Patients not enrolling in Stage 2: 99 - 117
2	Virtual Visit 8	18	126	Post-dose - 133
2	Virtual Visit 9	20	140	134 - 154
2	In-Person Clinic Visit 10	24	168	155 - 182
2	Virtual Visit 11	28	196	183 - 210
2	In-Person Clinic Visit 12	32	224	211 - 238
2	Virtual Visit 13	36	252	239 - 266
2	End of Treatment Visit 14	40	280	266 - 283

Primary Efficacy Endpoint Missing Data Imputation

For patients who do not have BMI value at the end of Stage 1 (Week 16), the unscheduled or early termination weight measurement mapped into Week 16 per visit window will be used for the primary analysis. If weights are measured in triplicate within a same date, the average of the triplicates will be calculated before the BMI calculation. The latest height value will be used together to derive the missing Week 16 BMI.

For patients who still do not have BMI value after above imputation at Week 16, they are treated as non-responder for the primary.

Missing or Partial Adverse Event and Medication Start or Stop Date:

For partial start dates:

- If the year is unknown, no imputation will occur.
- If the year is known and the month and day is unknown, then:
 - If the year matches the year of the first dose date, then impute the month and the day the same as first dose date.
 - If the year is not the same year of the first dose, then month and day will be imputed as 01 January.
- If the month and year is known and the day is unknown, then:
 - If the month and year match the month and year of the first dose date, then impute the day the same as first dose date.
 - If year and month is not the same as the first dose date, then the day will be imputed as "01".

For partial end-dates:

- If the year is missing, no imputation will be performed, and the AE/CM will be assumed as ongoing.
- If the year is present and both month and day are missing and the year is not the same as the last study date, then the month and day will be imputed as the last day of the year, 31 December.
- If the year is present and both month and day are missing and the year is the same as the last study date, then the month and day will be imputed as the last study date.
- If the year and month are present and only the day is missing, and the year and month is not the same as the last study day then the day will be imputed as the last day of the month.

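### Section 6.3 does not secure a Week 16 weight for patients who leave during Stage 1, and those with no weight in Days 99–117 are scored as non-responders under a treatment-policy estimand

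*Protocol*

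**What the plan says.** **Weights after leaving.** Protocol 6.3 asks patients who withdraw before Visit 14 to attend an Early Termination visit within 14 days (± 7) of the last dose. Table 1 schedules weight and height there. For a later weight: "If possible, patients will be asked to determine weight assessment at the expected time of their EOT visit".

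**When EOT falls.** Protocol 5.1.3.1 places it "on Study Day 112 for patients who complete only Stage 1 or on Study Day 280" for those who complete Stage 2. Section 5.2, writing about patients who discontinue, refers to the EOT visit of Day 280.

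**Who may be withdrawn.** Section 6.3 states: "Discontinuation of trial treatment or skipped visits/injections may be allowed without withdrawal from the trial". Its reasons for which an investigator may withdraw a patient from the trial include "Non-adherence to trial medication regimen or protocol requirements".

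**Patients who stop medication but stay.** Section 6.3 has them weighed at every visit, yet counts them as non-responders.

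**Lost to follow-up.** Section 6.4 requires sites to try to reschedule any missed evaluation, and asks for at least three contact attempts, "including at least 1 in relation to the final visit on Day 308".

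**Analysis.** For discontinuation of treatment, the SAP estimand table says: "Treatment policy strategy will be implemented". SAP V.E fills a missing Week 16 BMI from an unscheduled or early termination weight that maps to Week 16 (Days 99–117 for patients not entering Stage 2), combined with the latest height. If there is still no value, "they are treated as non-responder for the primary". SAP VII.A.1 restricts summary tables of weight to in-person measurements.

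**The concern.** Under treatment policy, the Week 16 weight is wanted whether or not the patient is still taking setmelanotide. The Stage 1 efficacy analysis uses everyone dosed, so leavers stay in the denominator. Each one therefore needs a weight near Day 112, and no section requires it.

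For a Stage 1 leaver, the later weight is optional and its date is unclear. If the site reads EOT as Day 280, the weight arrives too late for the primary analysis. Removing a patient from the trial for non-adherence ends scheduled weighing in people whose weights the estimand calls for.

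At stake is the meaning of the primary proportion. For leavers without an in-window weight, the analysis counts leaving as failure, while the SAP describes the effect regardless of discontinuation. In small gene cohorts a single patient moves the result visibly. A missed Week 16 weight cannot be recovered later.

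**Working it through.** The documents state no figure for dropout, power or expected response, so there is nothing to reproduce. The check has three parts.

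**1. Which date is EOT for a Stage 1 leaver?**

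- 5.1.3.1 gives Day 112 to those who complete only Stage 1 and Day 280 to those who complete Stage 2. A Stage 1 leaver has done neither.
- Under 5.1.2, the route to Stage 2 depends on the Week 16 BMI result, which the leaver does not have.
- 5.2 speaks of Day 280 for discontinuers, and the sentence in 6.3 just before the weight request refers to Visit 14, which is Day 280.
- Against the SAP window of Days 99–117: Day 112 is inside and Day 280 is outside.

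**2. Can the Early Termination visit fill the gap?** Let L be the day of last dose. The timing in 6.3 can be read as L+7 to L+21, or as L to L+21. The latest on-schedule visit is L+21 on both readings.

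- To reach Day 99: L + 21 ≥ 99, so L ≥ 78.
- With L = 77, the latest visit is 77 + 21 = Day 98, one day short.
- On the L+7 to L+21 reading, the visit also needs L + 7 ≤ 117, so L ≤ 110. It is certain to land in the window only if L + 7 ≥ 99 and L + 21 ≤ 117, that is L = 92 to 96.
- Table 1 prints ± 5 days for this visit. With L + 19 as the latest day, L must be at least 80, so the gap is slightly wider.

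So for a last dose on Days 1–77 (77/112 = 69% of Stage 1 days), an on-schedule Early Termination visit cannot supply the Week 16 value. This is a share of calendar days, not of expected leavers.

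**3. How large is the bias?** Let d be the share of dosed patients with no weight in Days 99–117 because they left, and r the share of them who would have met the 5% criterion. Non-responder scoring sets their contribution to zero, so

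bias = −d × r.

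| d (assumed) | r (assumed) | Understatement |
|---|---|---|
| 5% | 10% | 0.5 points |
| 10% | 20% | 2 points |
| 20% | 30% | 6 points |
| 30% | 50% | 15 points |
| any | 0% | 0 |

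At cohort level, the protocol aims for up to 10 patients per gene. If one leaver in 10 was truly a responder, 5/10 (exact 95% CI 18.7–81.3%) is reported as 4/10 (12.2–73.8%). If that leaver was not a responder, nothing changes. The shift per patient is smaller in cohorts that pool several genes to more than 10 patients, as the SAP's SEMA3 pathway and Other groups may.

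**The case against.** **The plan does not simply ask for the wrong weight.** A reader might infer that 6.3 collects EOT instead of Week 16. The documents do not support that. Randomization happens only at the Day 112 visit, so a Stage 1 leaver never enters Stage 2, and Day 112 is a natural reading: "The End of Treatment Visit will occur as an in-person clinic visit on Study Day 112 for patients who complete only Stage 1". What stands is that this sentence covers completers, 5.2 points the other way, and no text settles the date.

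**Nor is the weight simply uncollected.** The Early Termination visit is required, withdrawn patients are strongly encouraged to attend it, and SAP V.E uses its weight before any non-responder rule applies. Section 6.4 already has sites reschedule missed evaluations, which would include Day 112. What stands is that collection is not assured: the visit cannot reach the window after an early last dose, the later weight is optional, and the only dated contact attempt is tied to Day 308, which is 196 days after Day 112.

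**Withdrawal for non-adherence is not a flat contradiction.** A reader might infer that 6.3 reserves withdrawal for safety and then breaks its own rule. The retention language is an aim, and both the tolerance of skipped injections and the investigator's right to withdraw are permissive. They can coexist. What stands is the consequence: removal from the trial ends scheduled weighing.

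**Non-responder scoring is conservative, and no testing is planned.** Both are true. The direction is known, but a conservative estimate is still not the declared estimand.

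**The non-responder sentence in 6.3 may be meant for Stage 2.** It mentions treatment assignment, which exists only there, and the SAP's intercurrent event likewise names randomized treatment although the primary endpoint is in open-label Stage 1. Neither text limits its scope, so this too needs settling.

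**Conclusion.** The point holds as a gap in data collection with a consequence for the estimand. A Week 16 weight is not secured for patients who leave during Stage 1. Those without a weight in Days 99–117 are scored as non-responders, which departs from treatment policy and can only lower the estimated response rate.

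The day arithmetic follows from the documents and assumes that the Early Termination visit is on schedule. The size does not: it rests on assumed values of d and r. Moderate assumptions give 2 to 6 points, and the effect is zero if no lost patient would have responded. It would be wrong to treat every leaver as an outcome lost by default, because some will have an in-window weight.

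A related conflict belongs in the same correction. Patients who stop medication but remain are weighed throughout, and the protocol still counts them as non-responders while the SAP declares treatment policy. Unless that is reconciled, collecting a Day 112 weight from leavers may not change how they are scored. A possible difference between arms in Stage 2 removals is conceivable, but the documents give no figure for it and it does not touch the primary endpoint.

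This is an inexpensive improvement worth making, not a flaw that invalidates the primary analysis.

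**What to change.** 1. **Protocol 6.3 and 6.4, date of the weight.** For patients who leave during Stage 1 and have not withdrawn consent, request a weight at Day 112 (Days 99–117), in clinic or on the trial-issued home scale under observation. For those who leave during Stage 2, name Day 280. In 6.4, tie one documented contact attempt to Day 112 for patients lost in Stage 1.
2. **Protocol 6.3, stopping medication versus leaving the trial.** State that non-adherence alone does not end scheduled weight follow-up unless consent is withdrawn. Decisions on treatment stay with the investigator, and withdrawal for adverse events is unchanged.
3. **Protocol 6.3 and SAP, scoring.** Reconcile the sentence counting patients who stop therapy as non-responders with the treatment-policy strategy, and say which stage each statement covers.
4. **SAP V.E and VII.A.1.** V.E already accepts an unscheduled weight in the window. Add that an observed home-scale weight in Days 99–117 counts for the primary endpoint despite the in-person restriction on tables.

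**Cost.** Wording in both documents and one extra contact per leaver. Some values will come from a home scale and should be flagged. For a growing child, combining a new weight with the latest clinic height slightly overstates BMI, because that height is older and shorter. That errs toward understating response.

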6.4. Lost to Follow-up

Patients are considered as being lost to follow-up if they fail to return for scheduled evaluations and cannot be contacted by the site. The following actions must be taken if the patient fails to return to the clinic for a required trial evaluation:

- The trial site must attempt to contact the patient and reschedule the missed evaluation as soon as possible and counsel the patient on the importance of maintaining the assigned evaluation schedule.
- Before a patient is deemed lost to follow-up, the Investigator or designee must make every effort to regain contact with them or next of kin by, for example, repeat telephone calls, certified letter to the patient's last known mailing address, or local equivalent methods. At least 3 unique documented contact attempts to follow-up over a period of weeks to months should be made, including at least 1 in relation to the final visit on Day 308. The patient should only be permanently recorded as lost to follow-up if they did not respond to any contact attempts by Day 308. These contact attempts should be documented in the patient's medical records.

6.5. Lifestyle Counseling

6.5.1. Physical Activity

During the trial, patients will receive physical activity counseling by qualified site personnel and will be encouraged to perform aerobic physical activity for a duration of at least 150 minutes per week, maintaining an average target HR of 70% of their maximum HR. Aerobic physical activity includes repetitive motions of large muscle groups, such as brisk walking, swimming, mowing

the lawn, running, dancing, etc. Maximum HR is calculated as 220 beats per minute (bpm) minus patient's age in years.

Example: if a patient is 50 years old, the maximal HR is calculated as 220 bpm – 50 years of age = 170 bpm. For this patient, 70% of the maximal HR (0.70×170 bpm) is 119 bpm. Therefore, this patient will be encouraged to perform 150 min of aerobic physical activity per week targeting an average HR of 119 bpm.

Each patient will be provided with an electronic tracker to monitor HR and physical activity to inform whether the target level of physical activity was fulfilled. At every virtual and in-person visit, each patient will be asked if they performed the target level of activity.

6.5.2. Nutrition

During the trial, patients will receive dietary counseling by qualified site personnel and will be encouraged to follow a diet with a reduction of 500-750 kilocalories (Kcal) per day as advised by the American College of Cardiology (ACC), American Heart Association (AHA), The Obesity Society (TOS) 2013 guidelines (Jensen 2014). At each visit (virtual and in-person) patients will be counselled on nutrition and compliance will be assessed by on-site personnel.

6.5.3. Skin Protection

Skin hyperpigmentation, or tanning, was observed in the cynomolgus monkey toxicology studies and the human studies. These events were reversible upon cessation of trial medication. However, it is still uncertain if exposure to sunlight might exacerbate the tanning effects of setmelanotide. Therefore, patients will be advised to use sunscreen and/or to wear protective clothing to avoid excessive exposure of their skin to sunlight and to avoid sun-tanning.

It is also important that patients do not participate in any activities that will intentionally cause their skin to tan (e.g., visit ultraviolet [UV] tanning salons, use spray tanners, self-tanning lotions, etc.).

7. TREATMENT OF PATIENTS

7.1. Description of Trial Medication

All trial medication is for investigational use only and is to be used only within the context of this protocol. All investigational trial medication (setmelanotide and placebo) will be supplied by the Sponsor.

[REDACTED]

The reference therapy for the double-blind period of this trial is a placebo vehicle. [REDACTED]

[REDACTED]

[REDACTED]

Setmelanotide and placebo are clear, colorless to slightly opalescent solutions essentially free of visible particulates and are suitable for a double-blind trial.

7.2. Randomization, Blinding, and Unblinding

7.2.1. Stage 1

Stage 1 of the trial is open-label, and all patients will receive setmelanotide.

7.2.2. Stage 2

Patients who are eligible to enter Stage 2 of the trial will be randomized in a blinded manner on Day 112 (Stage 2 Entry Visit) in a 2:1 ratio to receive either setmelanotide (2) or placebo (1). The randomization schedule will be generated by the Sponsor or its designee, and trial personnel will use a web-based interactive response technology (IRT) system to obtain the randomization number for each eligible patient.

Stage 2 of this trial is double-blinded. The patient, Investigator, and Sponsor will be blinded to trial treatment.

7.2.3. Blinding and Unblinding

Full details for the blinding and unblinding are provided in the separate Blinding and Unblinding Plan.

Blinded randomization will occur via an IRT.

Emergency unblinding for AEs may be performed through an IRT. The IRT will be programmed with blind-breaking instructions. In case of an emergency, the Investigator has the sole responsibility for determining if unblinding of a patient's treatment assignment is warranted. Patient safety must always be the first consideration in making such a determination. If the Investigator decides that unblinding is warranted, the Investigator should make every effort to contact the Sponsor before unblinding a patient's treatment assignment unless this could delay emergency treatment for the patient. The date and reason for the unblinding by the Investigator must be recorded. If a patient's treatment assignment is unblinded, the Sponsor must be notified by the Investigator within 24 hours that an unblinding occurred. The Investigator should not reveal to the Sponsor the patient's treatment allocation unless the Sponsor requests this information for safety purposes.

For any unexpected SAE that is treatment-related (e.g., possible or probable), the blind will be lifted by the Sponsor only for that specific patient. The blind will be maintained for persons responsible for the ongoing conduct of the trial (such as the monitors, Investigators, etc.) and those responsible for data analysis and interpretation of results at the conclusion of the trial (such as biometrics personnel). Unblinded information will only be accessible to those who need to be involved in the safety reporting to Health Authorities, Independent Ethics Committees (IECs), and/or Institutional Review Boards (IRBs). Investigators will receive only blinded information unless unblinded information is judged necessary for safety reasons.

